7.4 Follow up

Patient data will be collected up to a minimum of 24 months post-CCTA. Clinical data will also be analysed for the 6 months pre-CCTA to ensure no cross over between diagnostic pathways and prior testing (including CCTA) within 6 months (Figure 1).

Longitudinal long-term follow-up (>2 years) at 5 and 10 years would be feasible and cost effective using the same methodology of HES downloads and data analysis. This would provide a true long-term perspective of health care resource use in a stable angina population

Figure 1 Study Design Overview

8 Statistical Methodology

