Liverpool Centre for Cardiovascular Science

The FISH&CHIPS Protocol

FFRCT In Stable Heart disease and Coronary Computed Tomography Angiography Helps Improve Patient care and Societal costs

Study Objective	The primary objective of FISH and CHIPS is to identify differences in health- related events, time to diagnosis and overall healthcare costs of a stable chest pain population undergoing Coronary Computed Tomography Angiography (CCTA) and Fractional Flow Reserve (FFR _{CT}), compared to a previous 'standard of care' diagnostic chest pain pathway of CCTA and non- invasive functional testing.	
Study Design	This is a multi-centre, retrospective, observational analytic cohort study design. The study will utilise the electronic health record (EHR) data already collected by NHS England on all patients that underwent a CCTA for the assessment of coronary artery disease over a 2-year period (April 2017-April 2019). All patients were treated in accordance with the latest NICE clinical guidance (CG 95 2016). Healthcare data will be collected from 6 months prior to and 12 months following the index CCTA. Hospital admissions data collected will include inpatient hospital admissions, outpatient visits, cardiovascular diagnostic tests and procedures. All subsequent clinical events including myocardial infarction and all-cause death will be measured as clinical outcomes. Costs are determined from the NHS national tariff system.	
Study Principal	[name]	
Investigator	Liverpool Heart and Chest Hospital and the University of Liverpool,	
	[name],	
	Liverpool,	
	[name]	
	United Kingdom	
Sponsor	Liverpool Heart and Chest Hospital,	
	[name],	
	Liverpool,	
	[name]	
	United Kingdom	
FISH	& CHIPS MRC Medical Research Council	

RESEARCH REFERENCE NUMBERS

IRAS Number:	285996
ISRCTN Number / Clinical trials.gov Number:	
FUNDERS Number:	MR/T024933/1

Medical MRC

Investigator Protocol Signature Page

The undersigned confirm that the following protocol has been agreed and accepted and that the Chief Investigator agrees to conduct the trial in compliance with the approved protocol and will adhere to the principles outlined in the Medicines for Human Use (Clinical Trials) Regulations 2004 (SI 2004/1031), amended regulations (SI 2006/1928) and any subsequent amendments of the clinical trial regulations, GCP guidelines, the Sponsor's (and any other relevant) SOPs, and other regulatory requirements as amended.

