3.1 Professional Summary

Protocol Title	FFRCT In Stable Heart disease & CCTA Helps
	Improve Patient care and Spending
Investigation strategy	CCTA plus FFRCT reduces healthcare resource
	utilization and costs compared to a CCTA
	strategy alone.
Study Principal Investigator	[name]
Academic Research Organization	Liverpool Centre for Cardiovascular Science
	(LCCS), Liverpool Heart and Chest Hospital,
•	Liverpool, UK
Sponsor	The University of Liverpool
Participants and Study sites	Approximately 100,000 patients from 25 sites
	who received a CCTA for the assessment of CAD
	in NHS England.
Study Planned Duration	36 months
Primary study objective	To determine whether a CCTA and FFRCT
	diagnostic pathway reduces health-related
	events, time to diagnosis and overall healthcare
	costs compared to a 'standard of care' CCTA
	diagnostic chest pain pathway.
Primary hypothesis	The addition of FFRCT into a CCTA diagnostic
	pathway will be safe with no difference in major
	adverse cardiovascular event rates or death
	whilst reducing the time to diagnosis, result in
	fewer downstream tests and reduce overall costs
	to the healthcare system.
Population	Chest pain patients with suspected stable
	coronary artery disease being clinically
	investigated with a CCTA in England.
Study Design and Methods	A pragmatic 'real world' multi-centre,
	retrospective, observational analytic cohort
	study design. All patients receiving a CCTA at
	institutions utilising FFRCT as part of NHS
	England's Innovation and Technology Payment
	(ITP) programme. Participants will be recruited
	from 1 year pre-ITP and the 2 years of the ITP
	programme. Patients will be followed up at a
	minimum of 24-months post CCTA for the pre-
Duine and Findle sint	defined primary and secondary endpoints.
Primary Endpoint	Primary and secondary outcomes measured:
	1. MI event rate, hospitalization for
	acute coronary syndrome, MI deaths
	and all-cause death.
	2. Downstream testing: numbers of

MRC Researc

	 non-invasive functional tests, and invasive coronary angiograms without revascularisation performed following the index FFRCT. 3. Cost analysis: Total cost to the NHS of the index test and all downstream investigations and hospital admissions. 	
Secondary Endpoint	 Time to diagnosis- Trust Referral to Treatment (RTT) time. 	
	 Qualitative assessment of the impact of the FFRCT health technology 	
Study follow up	Participants will be followed up to a minimum of 24 months	

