5.4.2 Imaging biomarkers

Using the list of CCTA originally provided by the sites, the participating centres PACS teams will send the anonymised CCTA datasets to the CTU data storage for future linkage to the outcome data provided by NHS Digital. This process will ensure that anonymity is preserved while providing for a valuable resource in terms of a large database of anonymised imaging datasets with outcome data. There will also be the opportunity to repeat the data capture from NHS Digital in future years to establish medium and long-term outcomes. The purpose of creating this repository of anonymised outcome and imaging data is to allow for future research projects into image analysis of CTA including deep learning algorithms, radiomics analysis, and biomechanical modelling of coronary arteries all with the goal to improving future risk stratification to better target therapeutic interventions.

6 Study Design

This is a multi-centre, retrospective, observational analytic cohort study design.

This pragmatic 'real-world' trial, is designed to utilise big data to answer practical health questions and determine clinical outcomes in a timely fashion. Randomized clinical trials (RCT's) in comparative effectiveness research (CER) have been considered the gold standard. These are however, subject to several problems, including cost, patient selection bias and slow translation of knowledge into practice. (Angus, 2015) This study design removes any patient treatment heterogeneity effect seen in RCT's by assessing the impact of a new intervention on a whole population. (Longford, 1999) by utilising the electronic health record (EHR) data already collected by the NHS. This trial will thus represent a true assessment of the effectiveness of a new health technology on a population basis in the current NHS system and will enable the rapid translation of research into clinical and health care policy decisions.

Participants will include all individuals who had a CCTA performed at an institute participating in the NHSE FFRCT ITP during 2018-2020. All CCTA 12 months prior to and up to 24 months following the

FISH&CHIPS

Medical Research Council

start of a FFRCT programme (total study period 36 months) will be assessed. The cohort from this population that received an FFRCT will be separately identified, with linkage to the NHS digital data outcomes. HeartFlow will provide FFRCT-specific data.

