NHS Digital's Data Access Request Service (DARS) will be queried to provide the patient episodes over the study period. NHSD collects national data sets containing details of all admissions, accident and emergency (A&E) attendances, and outpatient appointments at NHS hospitals in England. DARS will extract data from the following data sets:

- Emergency Care Data Set (ECDS)
- Hospital Episode Statistics Admitted Patient Care (HES APC)
- Hospital Episode Statistics Critical Care (HES CC)
- Hospital Episode Statistics Outpatients (HES OPC)
- Hospital Episode Statistics Accident and Emergency (HES AE)
- Diagnostic Imaging Dataset (DID)
- Medicines Dispensed in Primary Care Data Set (from NHS Business Authority)
- Civil Registration Deaths

These data sets will provide the following information:

- Patient demographics (such as age group, gender and ethnicity)
- Administrative information (such as dates and methods of admission and discharge)
- Geographical information; such as where patients are treated and the area where they live (post code).
- Medications (type, dose and whether processed)
- ICA and revascularisation data linked to patients.
- Incidence of downstream testing; stress echocardiograms, stress MRI or nuclear scintigraphy.

Costs will be calculated for all hospital attendances, diagnostic investigations and treatments from the published NHS England National Prices and Tariff workbook (2017-2019- HRG/OPEC codes) with the appropriate market forces factor applied. Health economic modelling will be performed by the University of Liverpool.

Referral to treatment (RTT) data is collected by each NHS trust for each patient. This data will be collected by the local research teams.

7 Study Population

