7.1 Setting and Target Population

The study population will include all patients that received a CCTA for symptoms suggestive of CAD at a participating institute, 12 months prior to the institutes first FFRCT study and up to 24 months

MRC

 $\mathcal{L}_{\mathcal{L}}$

FISH&CHIPS

following (total study period up to 36 months). The timeframe of study recruitment is dependent upon the starting time of each centre in the ITP programme. Centres that had a later start date (onboarding) will have a shorter recruitment period, with a minimum of 12 months. These centres represent the 'real-world' NHS hospitals that are a mixture of secondary and tertiary referral centres (not dedicated academic or research sites) with clinical experience in CCTA who have met the minimum quality standards set out by NHS England. Thus, the study population represents a true reflection of the current CCTA practice in the national population, reducing the potential effect of selection bias seen in many RCT's.

A study population of 85,292 patients received either CCTA analysis alone (standard of care group, n=75,361) or CCTA and Heartflow FFRCT analysis (FFRCT group, n=9,799) during the two years of the new technology being available to each site. The total study population over the 36 months is likely to be over 100,000.

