7.3 Exclusion Criteria

- Age <18 years
- Coronary artery calcium scoring alone
- CCTA in addition to a second CT investigation for a non-coronary indication (CT TAVI, CT aorta)

mam

Liverpool Centre for Cardiovascular Science

- Previous CCTA within 6 months
- Prior CABG / MI
- Entry into a separate FFRCT research study during the study timeframe

[figure not shown]

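### The protocol names no source beyond 6 months of prior records for its open-ended MI/CABG exclusion, and its 6-month repeat-scan rule lets one person enter both pathways

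*Protocol*

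**What the plan says.** **History of MI or CABG.** Protocol section 7.3 lists earlier CABG or MI as an exclusion and sets no time limit on it. The repeat-scan exclusion in the same list does have one: "Previous CCTA within 6 months". The front-page synopsis (Study Design) fixes the data window: "Healthcare data will be collected from 6 months prior to and 12 months following the index CCTA". Section 7.4 works with the same six months: "Clinical data will also be analysed for the 6 months pre-CCTA to ensure no cross over between diagnostic pathways". It gives prior testing, including CCTA, as a second purpose and does not mention MI or CABG. Section 6 says that NHS Digital's access service "will be queried to provide the patient episodes over the study period".

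**Entry to the cohort.** Section 6 takes "All CCTA 12 months prior to and up to 24 months following the" start of a site's FFRCT programme. Section 7.1 repeats the span ("following (total study period up to 36 months") and says that late-starting centres "will have a shorter recruitment period, with a minimum of 12 months". The synopsis uses the term index CCTA, but no section defines it as a person's first scan or bars re-entry.

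**Follow-up.** Section 7.4 sets at least 24 months after the CCTA. Section 8.2 starts the event clock at the CCTA and takes the primary cost comparison at 12 months.

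**The concern.** There are two separate problems.

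First, an exclusion without a time limit cannot be applied from six months of history. A patient with an MI two years before the scan meets the exclusion, yet that admission lies outside the window the protocol commits to. Such patients are likely to be at higher risk. If they stay in unevenly across eras or test groups, they bias a non-randomised comparison of events and costs.

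Second, the repeat-scan rule reaches back only six months inside a window of up to 36. Someone scanned before the site's FFRCT start, or scanned without FFRCT after it, can be scanned again more than six months later with FFRCT and qualify a second time under the other pathway. The groups are then not independent. Where the two follow-up windows overlap, the same death, MI, angiogram or cost is credited to both pathways, which dilutes the contrast.

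**Working it through.** The protocol gives no figure of its own to reproduce on this point. The check is mainly one of logic, with two illustrations on stated assumptions.

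**1. MI/CABG exclusion against the data window**

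| Item | Protocol | Reach back from the scan |
|---|---|---|
| Prior CABG or MI exclusion | 7.3 | no limit stated |
| Data collected | front-page synopsis | 6 months |
| Data analysed | 7.4 | 6 months |
| NHS Digital query | 6 | the study period; no earlier history named |
| Other source for MI/CABG history | none found | not stated |

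The exclusion reaches further than any history the protocol commits to.

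Illustration (assumption: past event dates spread evenly over H years). The share falling in the last six months is 0.5/H:
- H = 5: 0.5/5 = 10%
- H = 10: 0.5/10 = 5%
- H = 20: 0.5/20 = 2.5%

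These are shares of past events, not of the cohort.

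**2. Repeat entry across the programme start**

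Inputs: 12 months before and up to 24 months after site start (sections 6 and 7.1; 12 + 24 = 36, which agrees with the stated total); a six-month bar (7.3); 24 months of follow-up (7.4); 12-month costs (8.2).

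Assumption: the first scan falls u months before site start, uniform on 0 to 12, and the second v months after, uniform on 0 to 24 and independent of u. The gap is u + v, and the area of all date pairs is 12 × 24 = 288.

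- Blocked by the rule (u + v ≤ 6): 6²/2 = 18, and 18/288 = 6.25%.
- Pass the rule: 1 − 18/288 = 93.75%.
- Gap over 24 months (u + v > 24): 12²/2 = 72. Pairs that pass the rule and put the second scan inside the first scan's 24-month follow-up: (288 − 18 − 72)/288 = 198/288 = 68.75%.
- Pass the rule with a gap of at most 12 months, so that the 12-month cost windows overlap: u + v ≤ 12 has area 12²/2 = 72, and (72 − 18)/288 = 18.75%.

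With an assumed post-start period of only 12 months, the total area is 144. The rule then blocks 18/144 = 12.5%, and 87.5% pass. Simulation of both cases agreed with these areas.

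These are shares of possible date pairs among people scanned once in each era. The protocol gives no repeat-CCTA rate, so they do not convert into a number of patients.

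**The case against.** **The look-back sentence has another purpose.** Section 7.4 ties the six months to crossover and prior testing and does not say that MI/CABG is ascertained that way. Sites supply the CCTA lists (5.4.2) and local teams collect other data (6), so history may be screened at site. This stands. It rules out the stronger reading that the exclusion cannot be enforced at all; what remains is that the protocol names no method for it.

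**More than six months may be held.** A study-period query, read literally, gives a patient scanned late in the window well over six months of earlier episodes. This also stands, but the protocol commits to analysing only six, and patients scanned early would have less history than those scanned late. The reach would then differ between eras.

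**Figure 1 is not available here** and may bear on patient flow. Nothing is held against the plan for that.

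**Index-scan rules and comorbidity history are often left to the SAP.** For comorbidity this is right, and no finding is made on case-mix adjustment. Eligibility is different: section 7.3 fixes the repeat-scan rule, and section 7.4 claims a result that this rule does not deliver.

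**Counts.** A reader might infer a number of wrongly retained patients. With an assumed prevalence of 2% to 8% and 5% of past events captured, 0.95 × 0.02 × 85,292 = 1,621 and 0.95 × 0.08 × 85,292 = 6,482. With 5% prevalence and a three-fold event rate, also assumed, those retained would supply 0.0475 × 3/(0.95 + 0.0475 × 3) = 13.0% of events. None of these rates is in the protocol. Section 4.1 describes CCTA as first-line for patients without prior CAD, so referral should already remove many. The documents do not support these figures as estimates.

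**Double counting.** A reader might also infer that all later events count in both groups. They do so only where the two follow-up windows overlap.

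**Conclusion.** The point holds in two parts. The MI/CABG exclusion has no time limit, while the protocol commits to six months of prior data and names no other source; older events would be missed unless sites screen for them, which is neither stated nor ruled out. Separately, the repeat-scan rule as written allows one person into both pathways, so the look-back does not prevent crossover beyond six months.

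The effect on the results is unknown, because no prior-MI/CABG or repeat-CCTA rate is given. The only size that can be put on it is conditional: under uniform scan dates the rule blocks 6.25% of pre/post date pairs with a 24-month post-start period, or 12.5% with 12 months. The logical gap does not depend on these percentages. It should be corrected, since following the text as written could retain patients the protocol means to exclude and would permit duplicate entry.

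**What to change.** 1. **Index scan.** Define the index as the first eligible CCTA per NHS number in the study window, and count any later scan, with its cost, as a downstream test of that entry. This brings dual entry to zero and needs no new data, because linkage is already by NHS number (9.1.1).
2. **MI/CABG exclusion.** State its source. Either request a longer admitted-patient look-back in the HES APC extract already listed in section 6 (for example five years) and apply the exclusion over all of it, or specify a site-record check. In both cases apply the same reach to both eras.
3. **Wording.** Amend section 7.4 so that it claims only what the six-month window does.

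Cost: a larger extract and slightly fewer patients. Records are used without consent, and section 9.1.1 promises to keep patient information to the minimum needed. The longer look-back therefore needs matching approvals and a data-minimisation case; the case is that the history is required to apply the protocol's own exclusion. The five-year length is a suggestion, not a figure from the protocol.

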8.1 Sample size and Power calculation

As an observational analytic cohort study design, this trial requires no power calculation for estimates of effect. However, multiple previous studies have guided the sample size and estimates of expected clinical outcomes. Disease prevalence at CCTA can be estimated from SCOTHEART (n=4778), where the coronary arteries were normal in 37%, non-obstructive CAD in 38% and obstructive CAD in 25% of a UK population. The CONFIRM registry study showed in a contemporary US population of over 5000 patients investigated by CCTA that the annual event rate varied between 0.31% for normal coronary arteries to 2.06% in the instance of obstructive CAD (Leipsic et al., 2013). The international ADVANCE registry study of a patient population being investigated with FFRCT had cardiovascular event rates of 1.16% at 1 year. Thus, it is possible to estimate expected clinical outcome event rates and compare to actual observed events across the pathways to determine the safety of a UK CCTA pathway.

8.2 Statistical Analysis

Analysis of the primary end-point is based on the rate of adverse events (MACE) as a composite of all-cause death, myocardial infarction and invasive coronary angiography without revascularization. Event rates over time will be calculated using Kaplan-Meier methodology from the time of the CCTA. Cox proportional hazard ratios will be used to determine the odds ratio (OR) of receiving revascularization post FFRCT compared to other tests.

Time to diagnosis will be compared using an 'intention to diagnose analysis' by analysing groups according to their investigative test (FFRCT vs CCTA alone).

The primary cost analysis will include total patient pathway costs at 12 months, with comparison between the two testing strategies. The mean cost difference with 95% confidence intervals and P value will be calculated. Sub-analysis will categorise the total costs breakdown as; Investigations, hospital stay, procedural costs.

Cost sensitivity analyses will be applied to the modelling, looking at different cost utilities in the UK and regional variability.

9 Good Clinical Practice

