5.2 Secondary objective

5.3 Primary Endpoints:

1. Safety: Has the implementation of FFR_{CT} been safe?

End points: Myocardial infarction event rate, hospitalization for acute coronary syndromes and mortality (all-cause and cardiovascular).

2. Time to Diagnosis: Does FFR_{CT} reduce the time to diagnosis and treatment?

End points: Trust Referral to Treatment (RTT) time.

3. Downstream testing: Does FFR_{CT} reduce the number of downstream investigations and the number of overall invasive and non-invasive diagnostic tests?

End points: numbers of non-invasive functional tests, and invasive coronary angiograms without revascularisation performed following the index FFR_{CT} .

4. Cost analysis: Does the technology represent value for money?

End point: Total cost to the NHS of the index test, all downstream investigations, hospital admissions and outpatient visits.

5.4 Exploratory Endpoints:

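### The primary MACE composite in section 8.2 contradicts 5.3 and 3.1: it adds angiography without revascularisation, omits ACS hospitalisation, and so does not measure safety

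*Protocol*

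**What the plan says.** Protocol section 8.2 states: "Analysis of the primary end-point is based on the rate of adverse events (MACE"), and defines this as a "composite of all-cause death, myocardial infarction and invasive coronary angiography without revascularization". This is the only place where the protocol says what MACE consists of; the abbreviation list merely expands the acronym.

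Section 5.3 lists four primary endpoints. The first, safety, consists of "Myocardial infarction event rate, hospitalization for acute coronary syndromes and mortality (all-cause and cardiovascular"). The third, downstream testing, consists of "numbers of non-invasive functional tests, and invasive coronary angiograms without revascularisation" after the index test. The summary table in 3.1 makes the same split. Its first outcome includes hospitalisation for "acute coronary syndrome, MI deaths" and death from any cause, and angiography without revascularisation sits in its second outcome, on downstream tests.

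The primary hypothesis in 3.1 is that the FFRCT "pathway will be safe with no difference in major" cardiovascular events or death, together with fewer tests downstream and lower cost. Section 4.2 cites trial evidence that FFRCT lowers the number of inappropriate angiograms.

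The level of one endpoint also differs. Section 3.1 gives "Time to diagnosis- Trust Referral to Treatment" (RTT) as a secondary endpoint, whereas 5.3 lists RTT time among the primary endpoints.

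**The concern.** The study's main clinical claim is safety, framed as no difference in MACE or death. Section 8.2 adds to MACE an outcome that 5.3 classes as test use and that the protocol expects the new pathway to reduce. It also leaves out a safety outcome that both 5.3 and 3.1 name. If the composite is analysed as written, its components are expected to move differently: angiography down, death and MI unchanged. A flat or favourable composite then says little about death and MI, and the result that the protocol would read as evidence of safety could coexist with more of them.

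**Working it through.** **Definitions side by side**

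| Outcome | 3.1 | 5.3 | 8.2 composite |
|---|---|---|---|
| All-cause death | outcome 1 | safety | included |
| Cause-specific death | MI deaths | cardiovascular mortality | not named (covered by all-cause death) |
| MI | outcome 1 | safety | included |
| ACS hospitalisation | outcome 1 | safety | omitted |
| Angiography without revascularisation | outcome 2, downstream testing | endpoint 3, downstream testing | included |

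Sections 3.1 and 5.3 agree with each other on the last two rows, and 8.2 departs from both.

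**Direction, without any assumed rate**

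Write the composite rate as h + a, where h is the rate of death/MI and a is the rate of angiography without revascularisation, treated as non-overlapping. If a falls and h is unchanged, the composite falls. If a falls and the composite is unchanged, h has risen. A finding of no difference in this composite is therefore not evidence of no difference in death/MI when the pathway works as the protocol expects.

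**Size, as illustration only**

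The protocol states no figure for this composite, so there is nothing to reproduce. The inputs are:
- h = 1.16% at 1 year, from section 8.1. This is a registry rate of cardiovascular events in patients investigated with FFRCT, used here as a proxy for death/MI.
- a = 5%, range 2–10%. This is an assumption; the protocol gives no such rate.
- A 20% relative fall in a, and a 1.5-fold rise in h. Both are assumptions.

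The composite risk ratio is (1.5h + 0.8a)/(h + a). The fall in a that exactly cancels the rise in h is 0.5h/a. Here 1.5 × 1.16% = 1.74% and 0.5 × 1.16% = 0.58%.

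| a | Angiography share a/(h + a) | Composite, comparator | Composite, FFRCT pathway | Risk ratio | Cancelling fall in a |
|---|---|---|---|---|---|
| 2% | 63% | 3.16% | 1.74% + 1.60% = 3.34% | 1.06 | 0.58/2 = 29% |
| 5% | 81% | 6.16% | 1.74% + 4.00% = 5.74% | 0.93 | 0.58/5 = 11.6% |
| 10% | 90% | 11.16% | 1.74% + 8.00% = 9.74% | 0.87 | 0.58/10 = 5.8% |

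On death/MI alone the same scenario has a risk ratio of 1.74/1.16 = 1.50.

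Section 8.1 also gives annual event rates from 0.31% (normal arteries) to 2.06% (obstructive disease). With a = 5%, the cancelling fall runs from 0.5 × 0.31/5 = 3.1% to 0.5 × 2.06/5 = 20.6%. The least favourable corner (h = 2.06%, a = 2%) needs 1.03/2, about 52%.

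**The opposite direction**

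If angiography were 20% higher rather than lower in the FFRCT group, with a = 5% and death/MI equal, the composite would be 1.16% + 6.00% = 7.16% against 6.16%, a risk ratio of 1.16. That would be apparent harm with no difference in death or MI.

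**The case against.** The conflict between the sections is hard to dispute. It lies within the protocol, so a separate analysis plan would not remove it. The objections bear on what can be built on it, and several stand.

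- A reader might infer that angiography without revascularisation is far more common than death or MI and so decides the result. The protocol gives no rate for it. The shares of 63–90% above come from assumed rates, and the 20% fall is assumed too.
- A reader might infer that the composite must favour FFRCT. That depends on the comparison. Section 7.1 describes groups by test received (CCTA alone, n=75,361; CCTA plus FFRCT, n=9,799), and section 4.1 describes FFRCT as a second-line test for indeterminate or intermediate stenoses. CCTA-alone patients would include most of the normal scans, so angiography could be higher in the FFRCT group. Masking fits a comparison of the new pathway with the previous one better. Section 8.2 specifies grouping by test only for time to diagnosis.
- A reader might infer that deaths and MIs would go unseen. Section 5.3 still names them as endpoints, and nothing bars reporting them separately. But 8.2 describes no separate analysis of them, and the composite is what it attaches to the primary endpoint.
- Omitting ACS hospitalisation loses only ACS admissions that are not MI, since MI stays in. Using angiography both as a component and as an endpoint of its own is not in itself an error.
- Section 8.2 does not confine itself to one outcome: it also sets out a primary cost analysis and a time-to-diagnosis comparison. The weakness is the inconsistent level of RTT time, which is a secondary matter.
- Section 5.3 lists safety outcomes without combining them, so there is no composite there to copy word for word.

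**Conclusion.** The point holds. The primary composite in 8.2 contradicts 5.3 and 3.1 in two components, and because one of them is a resource-use outcome that the protocol expects FFRCT to reduce, the composite is not a measure of safety. That conclusion needs no outside figure. It carries high confidence.

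The size and direction of the distortion are less certain. Under the labelled assumptions, a 1.5-fold rise in death/MI appears as a composite risk ratio of about 0.93 with angiography at 5% and 0.87 at 10%. At 2% it is diluted to about 1.06 but not fully hidden. These figures rest on the 1.16% proxy, non-overlapping components, and assumed angiography rates and effect. The documents support saying that the composite can mask harm, or signal false harm under a by-test comparison; they do not support saying that it will do either.

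**What to change.** In 8.2, build the primary safety composite from the outcomes that 5.3 lists under safety: all-cause death, MI and ACS hospitalisation. Remove angiography without revascularisation from it and analyse that outcome only under downstream testing. State that all-cause death, cardiovascular death and MI are each reported separately.

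As a secondary matter, give RTT time one level and use one endpoint list in 3.1, 5.3 and 8.2. This includes choosing between MI deaths (3.1) and cardiovascular mortality (5.3). Whichever level RTT time takes, either 3.1 or 5.3 must change as well as 8.2.

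The cost is wording. Section 6 already requests hospital episodes, death registrations and linked angiography data. The downside is probably fewer composite events and so a wider interval, but on an outcome that addresses the safety hypothesis.
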